8.6. Safety Analysis

All safety data collected on or after the date that study drug was first dispensed through the Day 28 follow-up visit will be summarized by treatment group (according to the study drug received). Data for the pretreatment period will be included in data listings.

Summaries will be provided by group: 5-day dosing group or 10-day dosing group for Part A and Mechanically Ventilated Treatment Group or Extension Treatment Group for Part B.

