3.1. Endpoints

The primary endpoint of this study is:

- Clinical status assessed by a 7-point ordinal scale on Day 14

The secondary endpoint of this study is:

- The proportion of participants with treatment emergent AEs

Other endpoints of interest are:

- Time to SpO₂ > 94% on room air
- Time to first negative SARS-CoV-2 polymerase chain reaction (PCR)
- Duration of oxygen therapy (days)
- Duration of hospitalization (days)
- All cause mortality at Day 28
- Time to clinical improvement (days): Clinical improvement is defined as a \geq 2-point improvement from Day 1 on a 7-point ordinal scale

- The proportion of participants in the Mechanically Ventilated Treatment Group and Extension Treatment Group with treatment-emergent AEs

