3.4. Duration of Treatment

Participants will receive study treatment with RDV for 5 days (Treatment Group 1), 10 days (Treatment Group 2), 10 days (Mechanically Ventilated Treatment Group), or either 5 or 10 days (Extension Treatment Group). If the participant is discharged, RDV treatment will stop at that time.

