5.3. Dosage and Administration of Remdesivir

Remdesivir for injection, 100 mg, will be provided by Gilead. In Part A, participants in Treatment Groups 1 and 2 will receive RDV 200 mg on Day 1 followed by IV RDV 100 mg on Days 2, 3, 4, and 5. Participants in Treatment Group 2 will also receive RDV 100 mg on Days 6, 7, 8, 9, and 10. In Part B, participants in the Mechanically Ventilated Treatment Group will receive IV RDV 200 mg on Day 1 followed by IV RDV 100 mg on Days 2, 3, 4, 5, 6, 7, 8, 9, and 10. Participants in the Extension Treatment Group will also receive IV RDV 200 mg on Day 1 followed by IV RDV 100 mg on Days 2, 3, 4, 5, 6, 7, 8, 9, and 10 unless the 5-day dosing regimen used in Treatment Group 1 of Part A is selected. If treatment for 5 days is selected, all participants in the Extension Treatment Group and all new participants will be reassigned to receive treatment for a total of 5 days. Remdesivir treatment will be stopped at discharge regardless of the scheduled duration of therapy. Remdesivir will be administered over 30 minutes where possible.

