8.3.1.2. Safety

The primary analysis set for safety analyses is defined as the Safety Analysis Set, which will include all participants who (1) are randomized into the study and (2) have received at least 1 dose of RDV. Participants will be grouped according to the treatment to which they were randomized for Part A (5-day dosing group or 10-day dosing group) and according to the treatment to which they were assigned for Part B (Mechanically Ventilated Treatment Group or Extension Treatment Group).

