8.5.2. Secondary Analyses

The secondary endpoint of proportion of participants with treatment emergent AEs will be compared between the 2 treatment groups in Part A using a Fisher's Exact test. The point estimate of the treatment difference and the associated 95% confidence intervals will be provided. Secondary or other endpoints of interest related to proportion of participants will be compared between treatment groups in Part A using a chi-square test or Fisher's Exact test. Endpoints that are measured as time to first event will be compared between treatment groups using the Log-Rank test and continuous endpoints will be compared between treatment groups using a Wilcoxon rank sum test or analysis of variance model.

For Part B, summaries of the 7-point scale ordinal scale and other efficacy endpoints of interest will be provided by group (Mechanically Ventilated Treatment Group or Extension Treatment Group).

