8.6.1. Extent of Exposure

A subject's extent of exposure to study drug data will be generated from the study drug administration data. Exposure data will be summarized by group.

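### Does the protocol leave open whether Part A safety is grouped as randomized or by treatment received?

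*Protocol*

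**What the plan says.** Two places in the protocol describe how Part A participants are grouped for safety.

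- Section 8.3.1.2, which defines the Safety Analysis Set, groups participants by "the treatment to which they were randomized for Part A (5-day dosing group or 10-day dosing group"). Part B participants are grouped by the treatment assigned.
- Section 8.6 says that safety data "will be summarized by treatment group (according to the study drug received"). Its second paragraph continues: "Summaries will be provided by group: 5-day dosing group or 10-day dosing group for Part A", and it then names the two Part B groups.

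Three further sections bear on the reading. Section 3.1 gives one secondary endpoint: "The proportion of participants with treatment emergent AEs". Section 8.5.2 tests it with Fisher's exact test: the "proportion of participants with treatment emergent AEs will be compared between the 2 treatment groups in Part A". Section 8.6.1 adds "Exposure data will be summarized by group".

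The supplied SAP is restricted to Part B (SAP 1 and 2.2) and groups participants by baseline ordinal score (SAP 3.1.2 and 3.2). It gives no Part A rule. SAP 2.1.2 and 2.1.3 report the Part A analyses as already done.

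**The concern.** In many trials, grouping as randomized and grouping as treated differ only for the occasional dispensing error. Here the gap could be wider. Both arms get the same doses through Day 5, and the regimens part only afterwards: "Participants in Treatment Group 2 will also receive RDV 100 mg on Days 6, 7, 8, 9, and 10". Dosing also ends early for some people by design: "If the participant is discharged, RDV treatment will stop at that time". Someone randomized to 10 days and discharged by Day 5 has received no more than a 5-day course.

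If the parenthesis in 8.6 meant days dosed, such people would move to the 5-day group. Discharge, toxicity and death all occur after randomization and are plausibly linked to the risk of an adverse event. The only secondary comparison would then lose the protection of randomization, and the bias could run either way. With two rules in the protocol and no Part A SAP to hand, it is reasonable to ask which one governs.

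**Working it through.** **Step 1: can the parenthesis define groups at all?** Section 8.6 covers Parts A and B together. Section 3.3 gives remdesivir to all four groups. In Part A the drug is the same in both arms and only the planned duration differs. In Part B the two groups start with the same 10-day schedule and are separated by ventilation status. Read literally, the drug received separates nobody, and it cannot produce the four groups that the next paragraph of 8.6 names. The phrase has to be stretched to mean days dosed before it does anything.

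**Step 2: is there a days-dosed rule?** None is stated. Such a rule would have to place a 10-day participant who stopped after 6 to 9 doses, and a 5-day participant discharged on Day 3. Neither received a full course of either regimen. Sections 3.4 and 5.3 make stopping at discharge part of every regimen, and 6.11.1 lists discharge among the reasons for discontinuing study medication. Nothing treats it as a change of group. Section 8.6.1 also tabulates exposure by group, which would be partly circular if exposure defined the group.

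**Step 3: which text governs the tested endpoint?** The Fisher test is specified in 8.5.2, between the two Part A treatment groups. Sections 3.3 and 5.1.1 form those groups by 1:1 randomization. The parenthesis sits in 8.6, on how safety data are summarized, and does not redefine the arms in 8.5.2. The explicit membership rule is in 8.3.1.2, and 8.6 reuses the labels that 8.3.1.2 ties to randomization.

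**Step 4: what would be at stake under the other reading?** The plan has no figure to reproduce, because the documents give neither adverse event rates nor a share stopping by Day 5. The inputs below are therefore assumptions, apart from the 200 per arm in Protocol 8.9. Let p be the share of each arm that would stop by Day 5, r_e their event risk and r_o the risk in everyone else, with no true regimen effect.

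- As randomized: both arms have risk p·r_e + (1 − p)·r_o, so the difference is 0.
- Regrouped by days dosed: 200p people move. The 5-day group has 200(1 + p) people and risk [2p·r_e + (1 − p)·r_o]/(1 + p). The 10-day group has 200(1 − p) people and risk r_o.
- Difference (10-day minus 5-day) = [2p/(1 + p)] × (r_o − r_e).

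| p (assumed) | Group sizes (5-day/10-day) | 2p/(1 + p) | Gap of 10 points | Gap of 20 points |
|---|---|---|---|---|
| 5% | 210/190 | 0.10/1.05 = 0.095 | 1.0 | 1.9 |
| 10% | 220/180 | 0.20/1.10 = 0.182 | 1.8 | 3.6 |
| 20% | 240/160 | 0.40/1.20 = 0.333 | 3.3 | 6.7 |
| 30% | 260/140 | 0.60/1.30 = 0.462 | 4.6 | 9.2 |

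The last two columns are spurious differences in percentage points. The sign reverses if early stoppers have more events. The table shows why the question is worth asking. It does not estimate anything in this trial, because Steps 1 to 3 find no regrouping in the plan.

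**The case for a change.** The strongest case for a change is that the two statements do conflict. Section 8.6 is the operative section for safety, and nothing formally ranks 8.3.1.2 above it. That as-randomized was meant is an inference, because the protocol never says that the parenthesis is empty. The SAP declares no changes from the protocol's safety analysis (SAP 7.8), so the phrase stands uncorrected. The endpoint is formally tested, and deleting a few words would cost almost nothing.

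The inconsistency stands, and so does the point that regrouping by days dosed would be harmful. What does not stand is the step from a loose phrase to an open analysis choice. The inference is well supported: an explicit rule in the defining section, shared labels, a test between randomized arms, and no rule for counting doses. The absence of a Part A SAP adds little, since the supplied SAP was written for Part B only, and a separate Part A plan may exist. The sponsor's practice in the Part B SAP does not point to dose counting either. Actual treatment is derived from the baseline ordinal score (SAP Appendix 2, item 5), and people who stop early are tabulated as premature discontinuations (SAP 4.1).

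**Conclusion.** This is a clerical mismatch, not a gap that alters the analysis. Read as a whole, the protocol groups Part A safety as randomized. Under that reading the bias in the adverse event comparison is zero, so rewording 8.6 would change no result. It could not affect the Part A analyses in any case, because SAP 2.1.2 and 2.1.3 report them as complete.

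The conclusion rests on 8.3.1.2 governing group membership and on the Part A analysts having followed it. The documents supplied support the first. They cannot confirm the second, because the Part A analysis plan and outputs are not among them. The non-zero figures in the table apply only if both were wrong and the assumed inputs held.

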8.6.1. Extent of Exposure

A subject's extent of exposure to study drug data will be generated from the study drug administration data. Exposure data will be summarized by group.

8.6.2. Adverse Events

Clinical and laboratory AEs will be coded using the Medical Dictionary for Regulatory Activities (MedDRA). System Organ Class (SOC), High-Level Group Term (HLGT), High-Level Term (HLT), Preferred Term (PT), and Lower-Level Term (LLT) will be attached to the clinical database.

Events will be summarized on the basis of the date of onset for the event. A treatment-emergent AE will be defined as any AE that begins on or after the date of first dose of study drug up to the date of last dose of study drug plus 30 days, or up to Day 28, whichever is the later date.

Summaries (number and percentage of participants) of treatment-emergent AEs (by SOC, and PT) will be provided by group.

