6.5. Day 28 Follow up Assessment (±5 Days)

The following evaluations are to be completed if this visit is conducted in person. For participants who have been discharged from hospital, the final evaluation can be made by phone. Only AE and concomitant medication and ordinal scale (if discharged on or after Day 14) review are to be completed if visit is conducted by phone.

- Physical examination and vital signs (heart rate, temperature, blood pressure)

- Documentation of respiratory status:

Respiratory rate

- Oxygen supplementation: room air, low flow O₂ (L/min and %), high flow O₂ (L/min and %), CPAP/BIPAP (FiO₂ or %), mechanical ventilation (FiO₂ or %), ECMO

Oxygenation: SpO₂ or PaO₂

Radiographic findings (if available)

- Review AEs and document concomitant medications
- Review the Ordinal Scale (Section 6.9). If subject was not discharged by Day 14, any change in category and the date of any change in category from Day 14 to discharge (or Day 28) should be recorded

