7.3.3. Serious Adverse Events

All SAEs, regardless of cause or relationship, that occurs after the subject first consents to participate in the study (ie, signing the informed consent) and throughout the duration of the study, including the protocol-required post treatment follow-up period must be reported on the applicable eCRFs and Pharmacovigilance an Epidemiology (PVE) as instructed below in this section. This also includes any SAEs resulting from protocol-associated procedures performed after informed consent is signed.

Any SAEs and deaths that occur after the post-treatment follow-up visit but within 30-days of the last dose of study drug, regardless of causality, should also be reported.

Investigators are not obligated to actively seek SAEs after the protocol-defined follow-up period; however, if the investigator learns of any SAEs that occur after the protocol-defined follow-up period has concluded and the event is deemed relevant to the use of study drug, the investigator should promptly document and report the event to Gilead PVE.

All AEs and SAEs will be recorded in the eCRF database within the timelines outlined in the eCRF completion guidelines.

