7. SAFETY ANALYSES

Safety data will be summarized for the participants in the Expanded RDV-Treated Analysis Set. All safety data collected on or after the date that study drug was first dispensed through 30 days after last dose will be summarized by group for the Expanded RDV-Treated Analysis Set, unless specified otherwise. All safety data will be included in data listings.

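### Protocol 8.6 and 8.6.2 give different cut-offs for adverse events, and the 8.6.2 window, tied to last dose, runs up to 5 days longer in the 10-day arm of the Part A comparison

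*Protocol*

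**What the plan says.** **Two cut-offs in the protocol.** Section 8.6 takes safety data from first dispensing "through the Day 28 follow-up visit will be summarized by treatment group". Section 6.5 allows that visit a tolerance of 5 days either way. Section 8.6.2 instead defines a treatment-emergent adverse event as one beginning on or after first dose "up to the date of last dose of study drug plus 30 days, or up to Day 28, whichever is the later date".

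**Where the definition is used.** Section 8.5.2: "The secondary endpoint of proportion of participants with treatment emergent AEs will be compared between the 2 treatment groups in Part A". The test is Fisher's exact, with a difference and 95% confidence interval.

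**Dosing.** Sections 3.4 and 5.3 put the last scheduled dose at Day 5 (Treatment Group 1) or Day 10 (Treatment Group 2). Dosing ends at discharge if that comes first.

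**Collection.** Section 7.3.2 collects all adverse events through the required follow-up period, and 6.10 requires no assessments after Day 28. Section 7.3.3 extends reporting for one class only: "Any SAEs and deaths that occur after the post-treatment follow-up visit but within 30-days of the last dose of study drug". These should be reported, but the same section says investigators need not actively look for serious events once follow-up has ended.

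**SAP.** It covers Part B only. Its section 7 summarizes safety data "through 30 days after last dose will be summarized by group", and 7.8 states that nothing differs from the protocol's safety analyses.

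**The concern.** A programmer cannot apply 8.6 and 8.6.2 together: one stops at a visit, the other at a date set by the last dose. The choice also affects the randomized comparison. If 8.6.2 governs, the counting period depends on treatment length, which is what the arms were randomized to. The proportion with treatment-emergent events is the trial's only secondary endpoint and carries its safety objective. A window that can only be longer in the 10-day arm can only add events to that arm, and a simple comparison of proportions does not correct for this.

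**Working it through.** The documents state no end day for the window, so there is no printed figure to reproduce. The end day follows from the rule.

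**1. End of the 8.6.2 window.** End day = max(last-dose day + 30, 28). The earliest possible last dose is Day 1, giving max(31, 28) = 31, so the Day 28 term never decides the result. (If Day 28 meant the follow-up visit at its latest, Day 33, the term could matter only for a last dose on Day 1 or 2. Full courses are unaffected.)

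- Full course, 5-day arm: max(5 + 30, 28) = Day 35.
- Full course, 10-day arm: max(10 + 30, 28) = Day 40.
- Ratio 40/35 = 1.14, so the window is 14% longer.

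**2. Gap by the day on which dosing would stop, through discharge or otherwise.**

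| Stop day | 5-day arm ends | 10-day arm ends | Gap (days) |
|---|---|---|---|
| k = 1 to 5 | k + 30 | k + 30 | 0 |
| 6 | 35 | 36 | 1 |
| 7 | 35 | 37 | 2 |
| 8 | 35 | 38 | 3 |
| 9 | 35 | 39 | 4 |
| 10 or later | 35 | 40 | 5 |

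**3. Is the full gap rare?** On the protocol 8.9 planning figures, 4 + 7 + 13 + 16 + 20 = 60% of the 5-day arm are alive and in hospital on Day 14. Applying the odds ratio of 1.75 to the 10-day arm:

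- Odds of death: (0.02/0.98)/1.75 = 0.0117, or 1.2%.
- Odds of death or still in hospital: (0.62/0.38)/1.75 = 0.932, or 48.2%.
- Alive and in hospital: about 47%.

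Some of these may have stopped dosing early for other reasons, but the full gap is not an edge case.

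**4. Conflict with 8.6.** The follow-up visit falls between 28 − 5 = Day 23 and 28 + 5 = Day 33. Days 35 and 40 both lie beyond its latest permitted date.

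**5. What can fill the differing days.** Days 36 to 40 come after any permitted follow-up visit. Non-serious events are then mostly uncollected in both arms. Serious events and deaths can still arrive under 7.3.3, to Day 35 or Day 40 by arm.

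**6. A ceiling, not an estimate.** The documents give no event rates. Assume an equal constant hazard in both arms, full courses for all and complete capture, with incidence q by Day 35. The artefactual excess in the 10-day arm is (1 − q) − (1 − q)^(40/35). The last column is the chance of two-sided p < 0.05 with 200 per arm, by normal approximation.

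| Assumed q | Excess (points) | Chance of p < 0.05 |
|---|---|---|
| 5% | 0.7 | 6.1% |
| 20% | 2.5 | 9.4% |
| 50% | 4.7 | 15.6% |
| 70% | 4.7 | 18.5% |

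The maximum is at 1 − q = (7/8)^7 = 0.393, where the excess is 0.393 × (1 − 7/8) = 4.9 points. Step 5 shows that complete capture is not what the protocol provides, and step 2 that not everyone has the full gap. The real effect on the tested endpoint should be well below these figures.

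**The case against.** The strongest reply is that the asymmetry is mostly on paper. Routine collection stops at the same visit in both arms, and the tested endpoint is any treatment-emergent event, which most participants may already have had. All-cause mortality is fixed at Day 28 (protocol 3.1). If 8.6 governs the tables, the Day 35 versus Day 40 difference does not reach them. All of this stands, and it limits the size of the problem. It does not say which section governs.

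A second reply is that a fixed Day 28 cut brings its own imbalance: 28 − 5 = 23 days of post-dose observation after a full 5-day course against 28 − 10 = 18 after a full 10-day course. That is true. However, time since randomization is then equal, which is what a randomized comparison of durations needs.

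A third reply is that the SAP describes the Part A analyses as done, and no Part A SAP is among the documents, so a cut-off may have been set there. That cannot be checked.

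A reader might also infer more than the documents support:

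- **That late serious events are actively collected, so the tail is full.** Section 7.3.3 asks for reports but does not oblige investigators to seek them.
- **That serious events and treatment-emergent deaths are formally compared between arms.** No such Part A comparison is specified. The treatment-emergent death table is in the Part B SAP.
- **That the 10-day arm gains 0.5 to 2.5 points.** This comes from 1 − exp(−5 × rate) at assumed rates of 0.1% to 0.5% per day for late serious events or deaths. That is a different outcome, and the formula assumes full courses and complete capture. For deaths alone, the planning figure of 2% by Day 14 is about 0.14% per day.
- **That the SAP biases Part A.** It covers Part B, without formal testing. Its window of last dose plus 30 days matches 8.6.2 in effect and departs only from the general sentence in 8.6.

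**Conclusion.** The point holds as an unresolved contradiction between two protocol rules, together with an arm-dependent window for counting and reporting late serious events and deaths. The gap is 5 days for those dosed through Day 10, 1 to 4 days for those stopping on Days 6 to 9, and none for those stopping by Day 5. Its direction is known: any extra counted event falls in the 10-day arm. Its size cannot be derived from the documents. The effect on the proportion with any treatment-emergent event is probably small, given that routine collection ends at a common visit. A demonstrated bias against the 10-day arm is not shown. The contradiction is still worth removing, because treatment duration is the trial's question and the correction uses data already collected.

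**What to change.** 1. Reconcile protocol 8.6 and 8.6.2 so that one stated cut-off applies to each safety table, and delete the Day 28 clause that has no effect.
2. For the Part A between-arm comparison, count events with onset from first dose through study Day 28 in both arms.
3. Keep the tabulation to last dose plus 30 days as a descriptive supplement, so that late serious events and deaths stay visible.
4. If the Part A analysis is already complete, add the fixed-window re-tabulation and report it beside the existing one.
5. In SAP 7.8, record that the Part B cut-off of last dose plus 30 days differs from the general sentence in protocol 8.6.

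No change is proposed to the laboratory window in protocol 8.6.3, since required laboratory tests end at Day 14 or discharge.

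**Cost.** Wording and one extra table, with no new data. A few late events leave the compared table, and post-dose follow-up inside the window is shorter in the 10-day arm. Where the follow-up visit takes place before Day 28 (Day 23 at the earliest), routine collection will not cover the last days of the fixed window. The visit rule is the same in both arms.

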8.6.3. Laboratory Evaluations

Selected laboratory data will be summarized using only observed data. Data and change from baseline at all scheduled time points will be summarized.

Graded laboratory abnormalities will be defined using the grading scheme in DAIDS Table for Grading the Severity of Adult and Pediatric Adverse Event, Version 2.1 dated July 2017.

Incidence of treatment-emergent laboratory abnormalities, defined as values that increase at least 1 toxicity grade from baseline at any time post baseline up to and including the date of last dose of study drug plus 30 days will be summarized by treatment group. If baseline data are missing, then any graded abnormality (ie, at least a Grade 1) will be considered treatment-emergent.

Laboratory abnormalities that occur before the first dose of study drug or after the subject has been discontinued from treatment for more than 30 days will be included in a data listing.

CCI

[REDACTED]

[REDACTED]

